9.2 SAMPLE SIZE DETERMINATION

This study is a randomized, double blind placebo-controlled futility trial in which the primary outcome measure value (UMSARS total score) in a cohort of patients with MSA taking active agent will be compared to a known value from historical controls previously published in the literature. The primary outcome measure was used to calculate the sample size.

The primary statistical analysis will involve a comparison of the mean absolute difference in the active sirolimus group with a pre-specified fixed value, constituting a 4-point reduction in the expected mean increase in the UMSARS total score over 48 weeks without treatment. The expected mean increase in total UMSARS outcomes were obtained from the *U.S. Natural History Study of MSA* (n=96) (39), that reported that the total UMSARS score at 12 months increased a mean of 7.5 (SD: 8.4) absolute points from baseline. Also data from a phase III double-blind placebo-controlled 12-month clinical trial with rifampicin in MSA performed in the U.S. (40) (which was found to be ineffective to slow the progression of the disease) showed that in patients taking placebo (n=50) the total UMSARS score at 12 months increased a mean of 10.8 (SD: 10.7) absolute points from baseline. A weighted analysis of these two populations showed the pooled total UMSARS score at 12-months in patients with MSA in large studies performed in the U.S. had increased a mean of 8.6 (SD: 9.2) points from baseline.

Also, recent studies (38) have determined that the minimally clinically important difference (MCID) in the total UMSARS score is 3.5 points after 48-weeks from baseline.

Taking into consideration this MCID, for this trial, we will assume a promising difference in the UMSARS total score of 4 points between those taking active agent and the historical controls. Specifically, our null hypothesis is that patients receiving sirolimus will have a UMSARS total score progression of only 4.6 points at week 48 higher than baseline, compared to a progression of 8.6 points at week 48 from baseline reported in historical controls from natural history studies and placebo-controlled trials of MSA. Our alternate hypothesis is that sirolimus will be futile to slow the progression of the disease in patients with MSA. The statistical definitions are as follows:

$H_0: \theta_E - \theta_p \leq 4$ where $\theta_p = 8.6$ points increase at week 48 from baseline described in historical controls

$H_0: \theta_E \leq 4.6$ points increase at week 48 from baseline

$H_1: \theta_E > 4.6$ points increase at week 48 from baseline

Therefore, assuming an alpha of 0.05, and a power of 0.8 (one sided, as patients with MSA have not been reported to improve spontaneously) to detect a progression of 4.6 points (i.e., 8.6 minus 4) in the UMSARS total score after 48-weeks from baseline we will need to enroll 38 patients in the active agent arm. Anticipating a 10% for dropouts rate, we will need to enroll 42 patients in the active agent arm.

This trial will include a placebo group to facilitate blinding in a 3:1 proportion. However, statistical comparisons for the primary and secondary efficacy outcome measures will be performed between the active agent arm and the historical controls. We will therefore enroll 14 patients in the placebo arm.

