	a: Albumin, alkaline phosphatase, total bilirubin, bicarbonate, BUN, calcium, chloride, creatinine, glucose, potassium, total protein, AST, ALT, sodium. B: Serum pregnancy test (women of childbearing potential). c: 24-hour urine collection at baseline will be performed only if the baseline visit occurs > 30 days from the 24-hour urine assessment performed as part of the screening visit. d: Sirolimus blood level should be drawn 7 days after previous dose adjustment has taken place. e: If baseline visit (Visit 2) occurs within 15 days of the screening visit, the selected procedures can be foregone and the results of the screening day will be used. S: In-site visit at NYU (denoted in grey) SL: Safety labs visit, this can be done either at NYU or locally. If done locally, a phone call will be performed to inquire about adverse events. Safety labs should be drawn after a light (low fat) breakfast. P: Phone call or video-conference call																		

	Screening (V1) Day -42 to -1
Procedures	Baseline / Random. Visit 2 Day 1
	Study Visit 3 Day 7 +3 day
	Study Visit 4 Day 14 + 3 day
	Study Visit 5 Day 21 +3 day
	Study Visit 6 Day 28 +3 day
	Study Visit 7 Day 56 +15 day
	Study Visit 8 Day 84 +15 day
	Study Visit 9 Day 112 +15 day
	Study Visit 10 Day 140 +15 day
	Study Visit 11 Day 168 +15 day
	Study Visit 12 Day 196 +15 day
	Study Visit 13 Day 224 +15 day
	Study Visit 14 Day 252 +15 day
	Study Visit 15 Day 280 +15 day
	Study Visit 16 Day 308 +15 day
	End of study V17 Day 336 +15 day
	Phone followup V18 Day 350 +/-5 day
	Safety assess. V19 Day 365 +/-5 day
	CPK: Creatine Phosphokinase

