4 STUDY DESIGN

4.1 OVERALL DESIGN

To determine whether to test sirolimus in a large phase 3 trial, we propose to conduct a clinical trial of sirolimus in MSA using a futility design. A futility design under the null hypothesis assumes that sirolimus will slow the progression of the disease, whereas the alternative hypothesis assumes no benefit of sirolimus. If the null hypothesis is rejected (i.e., futility of sirolimus to slow progression of MSA), major phase 3 studies will be discouraged, whereas non-futility will offer strong support for a phase III trial to detect clinical efficacy.

To test this hypothesis we will perform a single-center, randomized, double blind, placebo-controlled, phase-II, futility trial, chosen as an efficient approach to determine if sirolimus would be worthy of future investigation in larger, more definite trials. This trial was designed to compare the mean value for the primary outcome measure, change in total Unified Multiple System Atrophy Rating Scale (UMSARS) score from baseline to week 48, between the sirolimus arm and a pre-specified fixed value, representing a 4-point reducing in the expected mean decline without treatment; this fixed value was obtained using data from previously completed a large natural history study(39) and the placebo arm of a recently completed clinical trial in MSA (40). The 4-point reduction was based on the recently reported minimally clinically important decline (MICD) in the total UMSARS score of 3.5-points (38).

The null hypothesis is that sirolimus will reduce the mean decline in the total UMSARS score over 12 month by, at least 4-points, compared with the expected (fixed) value obtained from the historical controls. If the null hypothesis is rejected, then the drug would be considered futile for further investigation in MSA. If the null hypothesis is not rejected, sirolimus would be considered for a phase 3 clinical trial.

Thus, the primary goal is to evaluate the effect of sirolimus on progression of MSA, including autonomic, cerebellar and parkinsonian features as measured by the UMSARS, a relevant clinical measure of disease progression. Secondary goals are to determine if there is any effect on neuroimaging (brain MRI) and ophthalmological (retinal OCT) biomarkers of the disease. As exploratory aim we will determine if there are any changes in plasma α Syn exosomes, as surrogate markers of autophagy.

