Follow-up phone call: Patients will be contacted 14 days (+/- 5 days) after the End of Study visit to follow up on and record any Aes that were ongoing at the end of their previous visit (Study Visit 18). The follow-up visit may be conducted over the phone; however a response from the patient should be obtained. This response may be obtained by a phone call with the patient and appropriately documented in the source notes. In the event that the patient is unreachable by phone, all reasonable efforts should be made and documented before considering the patient lost to follow-up.

Safety assessment: Assessment of safety will be conducted on-site 30 days (+/- 5 days) after the End of Study visit (Study Visit 19). We accept a visit window of 3 days before or after the target date. The following safety laboratory assessments will be performed:

- CBC, CMP, CPK (8 ml of blood) and urinalysis with 24-hour urine collection
- Lipid panel (2 ml of blood)
- Adverse event reporting

Alternatively, these safety lab assessments can be performed locally (e.g., at a local laboratory near the subjects’ home). In this case, the PI or a licensed research member of the team will provide the patient with a prescription for the required tests. Also, a research nurse or study manager will perform a phone call for adverse event reporting.

Unscheduled visit: An un-scheduled visit may be performed in-office or locally, should the investigators determine the need for so. The following safety laboratory assessments may be performed:

- CBC, CMP, CPK (8 ml of blood) and urinalysis with 24-hour urine collection
- Lipid panel (2 ml of blood)
- Sirolimus levels in blood (5 ml of blood)
- Adverse event reporting

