9 STATISTICAL CONSIDERATIONS

9.1 STATISTICAL HYPOTHESES

Primary Efficacy Endpoint: We hypothesize that treatment with sirolimus will show promise to slow the progression of the disease of patients with MSA. Specifically, our null hypothesis is that patients receiving sirolimus will have a UMSARS total score progression of only 4.6 points at week 48 higher than baseline, compared to a progression of 8.6 points at week 48 from baseline reported in historical controls from natural history studies and placebo-controlled trials of MSA. Our alternate hypothesis is that sirolimus will be futile to slow the progression of the disease in patients with MSA. The statistical definitions are as follows:

$H_0: \theta_E - \theta_p \leq 4$ where $\theta_p = 8.6$ points increase at week 48 from baseline described in historical controls
 $H_0: \theta_E \leq 4.6$ points increase at week 48 from baseline
 $H_1: \theta_E > 4.6$ points increase at week 48 from baseline

Secondary Efficacy Endpoints:

Brain MRI: We hypothesize that treatment with sirolimus will slow the increase of putaminal diffusivity in patients with MSA. Specifically, our null hypothesis states that patients receiving sirolimus will have a putaminal Trace (D) total score progression of 0.030×10^{-3} mm²/sec or less at week 48 versus baseline, compared to a progression of 0.070×10^{-3} mm²/sec at week 48 from baseline reported in specific longitudinal studies of MSA (41).

$H_0: \theta_E - \theta_p \leq 0.04$ where $\theta_p = 0.07$ ($\times 10^{-3}$ mm²/sec) increase in putaminal diffusivity at week 48 from baseline described in specific studies
 $H_0: \theta_E \leq 0.03$ points increase at week 48 from baseline
 $H_1: \theta_E > 0.03$ points increase at week 48 from baseline

Optical coherence tomography: We hypothesize that treatment with sirolimus will slow the thinning of the retinal nerve fiber layer (RNFL) in patients with MSA. Specifically, our null hypothesis states that patients receiving sirolimus will have a RNFL thickness thinning of 1.45 μ m at week 48 versus baseline, compared to a decrease of 3.7 μ m at week 48 from baseline reported in specific longitudinal studies of MSA (12).

$H_0: \theta_E - \theta_p \leq 2.25$ where $\theta_p = 3.7$ μ m decrease in RNFL at week 48 from baseline described in specific studies
 $H_0: \theta_E \leq 1.45$ μ m decrease at week 48 from baseline
 $H_1: \theta_E > 1.45$ μ m decrease at week 48 from baseline

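### The 8.6-point untreated reference is a 12-month change labelled as week 48, and the final UMSARS day is stated inconsistently, so the 4.6 futility threshold may not match the interval measured

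*Combined protocol and SAP*

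**What the plan says.** **The reference.** Section 9.2 takes a natural history study (n=96, mean change 7.5, SD 8.4) and the placebo arm of an earlier trial (n=50, mean change 10.8, SD 10.7). Both changes are given at 12 months. The weighted analysis "showed the pooled total UMSARS score at 12-months in patients with MSA in large studies performed in the U.S. had increased a mean of 8.6" points, with SD 9.2.

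**Its use.** The same section describes the fixed comparator as "constituting a 4-point reduction in the expected mean increase in the UMSARS total score over 48 weeks without treatment". Section 9.1 sets 4.6 points on sirolimus against 8.6, in the words "compared to a progression of 8.6 points at week 48 from baseline reported in historical controls". Section 4.1 states the same null hypothesis over a different period: "sirolimus will reduce the mean decline in the total UMSARS score over 12 month by, at least 4-points". Nothing links the two periods.

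**The final visit.** The schedule in section 1.3 has "End of study V17 Day 336 +15 day" and then "Phone followup V18 Day 350 +/-5 day". Section 4.1 says of that call: "Patients will be contacted 14 days (+/- 5 days) after the End of Study visit". Since 350 - 14 = 336, the call is counted from Day 336. Section 4.1 also places the month-12 clinic visit at Day 363 (+/- 10 days). Its paragraph on scheduled site visits has Visit 17 at month 12 after the start of study drug (+ 15 days), and its end-of-study paragraph allows 15 days either side.

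**The baseline.** If the baseline visit follows screening closely, "the selected procedures can be foregone and the results of the screening day will be used". This covers the UMSARS. The limit is within 15 days in section 1.3 and less than 14 days in section 4.1.

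**The concern.** The primary decision compares one arm with one fixed number, so that number has to describe the interval over which the arm is measured. If patients are assessed before 12 months and untreated worsening is smaller by then, a threshold of 4.6 asks for less than a 4-point benefit, and an inert drug escapes futility more often. If they are assessed after 12 months, the threshold asks for more than 4 points. The placebo arm (n=14) checks the historical value only descriptively (section 4.1). It enters the interim rules in section 9.4.5 but does not correct the final threshold. At stake are the real error rates of the go or no-go decision.

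**Working it through.** **Inputs** (sections 9.2 and 9.4.2): reference 8.6, SD 9.2, threshold 4.6, one-sided alpha 0.05, stated power 0.80, one-sample t-test, 38 patients before dropout and 42 enrolled on sirolimus. In this design, power is the chance of declaring an inert drug futile.

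**1. The plan's own figures.**
- Mean: (96 x 7.5 + 50 x 10.8)/146 = 8.63. This reproduces 8.6.
- SD: (96 x 8.4 + 50 x 10.7)/146 = 9.19. This reproduces 9.2; pooling the variances gives 9.25.
- Sample size, normal formula: (9.2 x (1.645 + 0.842)/4)^2 = 32.7, so 33.
- Sample size, exact t: power is 0.799 at n=34, 0.809 at n=35 and 0.838 at n=38. The stated 38 is therefore not the number for 0.80. It is conservative, and this is a separate matter from the interval.

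**2. What 4.6 asks for at other intervals.** The documents give no 48-week historical value. As an assumption, let untreated change be linear in time and take 12 months as 365 days (using 364 moves power by no more than about 0.005). Then:
- untreated change at day d = 8.6 x d/365
- benefit implied by the threshold = that change - 4.6
- power = chance that a one-sided t-test against 4.6 rejects when the drug is inert.

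The range in each row covers SD held at 9.2, scaled with the square root of time, or scaled linearly (at Day 336: 9.2, 8.83 and 8.47).

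| Mean interval (days) | Source | Untreated change | Implied benefit | Power, 38 completers |
|---|---|---|---|---|
| 336 | section 1.3 target | 7.92 | 3.32 | 0.70-0.77 |
| 343.5 | middle of its +15 window | 8.09 | 3.49 | 0.74-0.79 |
| 351 | end of that window | 8.27 | 3.67 | 0.78-0.81 |
| 363 | section 4.1 clinic visit | 8.55 | 3.95 | 0.83 |
| 365 | unscaled plan | 8.60 | 4.00 | 0.84 |
| 372.5 | middle of calendar month 12 +15 | 8.78 | 4.18 | 0.85-0.87 |
| 380 | end of that window | 8.95 | 4.35 | 0.87-0.89 |

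If all 42 complete, Day 336 gives 0.74-0.80. With 38 completers, power falls below 0.80 only if the mean interval is under about 348-356 days, depending on the SD scaling.

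**3. Sensitivity to linearity.** If change grew with the square root of time, the Day 336 value would be 8.6 x sqrt(336/365) = 8.25, and power would be 0.775 (n=38, SD 9.2).

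**4. Scale of the shift.** 8.6 - 7.92 = 0.68 points. The standard error of the reference is 9.2/sqrt(146) = 0.76.

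**5. Literal reading of section 9.4.2.** That section declares futility when 8.6 minus the observed mean is 4 or less, which can be read as a rule on the point estimate. With standard error 9.2/sqrt(38) = 1.492, an inert drug is called futile with probability Phi(4/1.492) = 0.996 at 365 days and Phi(3.317/1.492) = 0.987 at 336 days.

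**6. What a rescaled threshold would do.** 7.92 - 4 = 3.92. With n=38 and SD 9.2:
- If progression is linear, power against 3.92 returns to 0.838.
- If the untreated change at Day 336 really is 8.6, a true 4-point drug (mean 4.6) is wrongly called futile 11.6% of the time instead of 5%.
- If progression is linear and 4.6 is kept, that error falls to 1.8%, at the price of the power shown above.

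**The case against.** The sponsor can fairly say that the endpoint is labelled week 48 almost throughout, that the schedule agrees with it, and that Day 363 breaks section 4.1's own pattern of 28-day months (Days 84, 168, 252), so it may be a slip. That stands: the interval is inconsistently stated rather than wholly undefined. It does not repair the reference, which remains a 12-month figure.

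The low powers also need several conditions together: linear progression, a mean of exactly 336 days and 38 completers. The windows in the schedule and in the site-visit paragraph run only forwards. Using the screening UMSARS as baseline lengthens the interval, as does drug mailed up to 30 days after baseline when visits are timed from the start of drug. Section 5 says that later-stage patients progress only modestly. This compares stages and does not establish a within-patient curve, but if progression slows, the loss at Day 336 shrinks. The shift is also small beside the 3.3-point gap between the two sources (10.8 - 7.5). All of this limits the size and leaves the textual conflict in place.

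A reader might infer that the trial is underpowered, or that the threshold is lenient. The documents support neither as a general statement, because at calendar month 12 plus the window the threshold becomes stricter than intended. Nor do they support the inference that the reference must be rescaled. Linearity is not stated anywhere, and keeping 4.6 is defensible.

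**Conclusion.** A 12-month change is presented as a week-48 change reported in historical controls, and the last UMSARS day is given in incompatible ways. Both points are certain from the text. The consequence is conditional. Under linear progression, a t-test against 4.6 and 38 completers, power runs from 0.70-0.77 at 336 days, through 0.83 at 363 days, to 0.85-0.89 at 372-380 days, so the direction cannot be fixed until the visit day is. Under the literal point-estimate rule the effect is negligible. The stated sample size of 38 does not follow from its inputs, but it errs on the safe side. Severity is minor to moderate.

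**What to change.** 1. Reconcile sections 1.3, 4.1 and 9.1 to one target day and window for the final UMSARS and one period in the null hypothesis. State which UMSARS, screening or baseline visit, starts the interval.
2. If the final day is at 12 months, keep 8.6 and 4.6 and relabel them as 12-month values. If it is Day 336, stop describing 8.6 as a reported week-48 value, state the assumption that links 12 months to 48 weeks, and pre-specify a sensitivity analysis with a time-scaled reference (for example 7.92, threshold 3.92). Making the scaled value primary is a choice for the sponsor, given the possible rise in wrongful futility from 5% to about 12%. If it is made primary, carry it into section 9.4.2 and reconcile it with the interim cut-offs in section 9.4.5.
3. Restate section 9.2: for a 4-point gap, SD 9.2 and one-sided alpha 0.05, 35 evaluable patients give power 0.81 and 38 give 0.84.

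The cost is wording plus, for Day 336, one extra analysis. No additional patients are needed.

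### The 38 sirolimus patients in Section 9.2 do not follow from the stated inputs (35 do), and the 0.8 power is attached to the null value of 4.6 instead of 8.6

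*Combined protocol and SAP*

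**What the plan says.** Section 9.2 pools two historical groups and reports that the 12-month UMSARS total score "had increased a mean of 8.6 (SD: 9.2) points from baseline". It then says "we will assume a promising difference in the UMSARS total score of 4 points", which puts the boundary of the futility null hypothesis at 8.6 − 4 = 4.6: H0 is a mean increase of 4.6 or less, H1 a mean increase above 4.6.

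The sample size is derived "assuming an alpha of 0.05, and a power of 0.8", described as "one sided, as patients with MSA have not been reported to improve spontaneously". The power is said to be "to detect a progression of 4.6 points (i.e., 8.6 minus 4) in the UMSARS total score", and the result is "we will need to enroll 38 patients in the active agent arm". The enrolment target follows: "Anticipating a 10% for dropouts rate, we will need to enroll 42 patients in the active agent arm". Fourteen placebo patients are added by the 3:1 ratio; they play no part in the primary comparison.

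Section 9.2 names no formula or software. Section 9.4.2 names a one-sample t-test.

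**The concern.** Two things in the sample size statement look wrong.

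First, every input to a one-sample calculation is given, yet the result is not 38. Either the power or the SD actually used differs from the one written, and a reader cannot tell which. Section 4.2 says the study population was selected on this calculation, so it should be reproducible.

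Second, the 0.8 is attached to 4.6. In this design rejecting H0 means declaring sirolimus futile, and 4.6 is the edge of H0, where the chance of rejection is alpha. Taken literally, the sentence promises an 80% chance of discarding a drug that delivers exactly the hoped-for 4-point benefit. A reader used to efficacy trials might instead take it as 80% power to show benefit. It should mean neither. Whoever decides on phase III needs two numbers: the chance of wrongly discarding a drug that achieves 4.6, and the chance of discarding one that does nothing (8.6). Section 9.2 gives neither clearly.

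**Working it through.** **Inputs.** All are from Section 9.2 except the test, which is from Section 9.4.2.
- One-sided alpha 0.05: z = 1.645
- Power 0.80: z = 0.842
- Distance between 4.6 and 8.6: 4 points
- SD: 9.2
- Test: one-sample t-test

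**Step 1: the historical values.**
- Weighted mean: (96 × 7.5 + 50 × 10.8)/146 = 8.63
- Weighted average SD: (96 × 8.4 + 50 × 10.7)/146 = 9.19
- Pooled within-group SD: 9.25
- Total SD, including the difference between the two means: 9.35

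The stated 8.6 and 9.2 are reproduced by the weighted averages, so the pooling does not explain the discrepancy.

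**Step 2: trying to reproduce 38.**

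Normal approximation: n = ((1.645 + 0.842) × 9.2/4)² = 32.7, so 33.

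Exact noncentral t, with noncentrality (4/9.2)√n:

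| n | power at a true increase of 8.6 |
|---|---|
| 34 | 0.799 |
| 35 | 0.809 |
| 38 | 0.838 |

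The required n is therefore 35. The stated 38 is not reproduced.

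**Step 3: what would give 38.**
- A larger SD: by exact t at 80% power, 38 is required for SDs of about 9.6 to 9.7.
- A higher power: by the normal formula at 85%, ((1.645 + 1.036) × 9.2/4)² = 38.03. With the unrounded weighted SD of 9.188 it is 37.93, which rounds up to 38. This is the closest match, but the section states 0.8.
- A two-sided test does not give it: 42 by the normal formula, 44 by t.
- The total SD of 9.35 gives 36 by t. A Wilcoxon adjustment (35/0.955 = 36.6) gives 37.

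**Step 4: where the power applies.** Take a t-test of H0: mean increase ≤ 4.6, with n = 38 and SD 9.2. The standard error is 9.2/√38 = 1.49 and the one-sided 5% critical t on 37 degrees of freedom is 1.687. H0 is rejected when the observed mean exceeds about 4.6 + 1.687 × 1.49 = 7.12 (with the sample SD at 9.2).
- True mean 4.6: probability of rejection 0.05, by construction.
- True mean 8.6: probability of rejection 0.838.

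The stated 0.8 can only refer to 8.6.

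**Step 5: the rule in Section 9.4.2.** That section describes a t-test against 8.6, then rejects H0 whenever 8.6 minus the observed mean change is 4 or less, that is, whenever the observed mean is 4.6 or more. That is a rule on the point estimate. At a true mean of 4.6 the observed mean falls above 4.6 about half the time, so rejection is about 0.5, not 0.05. The 0.05 and 0.84 of Step 4 therefore belong to a t-test against 4.6, which is the test that Section 9.2 implies.

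**The case against.** The strongest reply is that nothing of consequence changes. The gap is three patients in the safe direction: 38 gives 0.838 where 0.80 was promised. The plan may have used 85% power or a small margin without saying so. The power sentence carries the bracket showing 8.6 minus 4 and follows directly on H0 and H1, so an informed reader can see that the 4-point distance was meant, and no computed number depends on the wording. All of this stands as far as size and adequacy go. It does not make the stated n follow from the stated inputs, and it does not make 4.6 the value at which power is 0.8.

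A second reply also stands, and limits the fix. The figures 0.84 and 0.05 assume a t-test against 4.6, which Section 9.4.2 does not at present describe. Section 9.4.5 adds an interim look when 24 patients have completed, with stopping for futility at an observed mean increase of 7 or more and for efficacy at 4 or less; that also alters the probabilities. Section 9.3 analyses randomised subjects with at least 3 months of drug, and Section 9.4.2 imputes missing data, so the number analysed is not simply enrolment less 10%.

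A reader might go further and infer that the 42 is wrong, because 38/0.9 = 42.2 rounds up to 43 while 38 × 1.1 = 41.8 gives 42. The documents do not support treating this as an error: 42 × 0.9 = 37.8 expected completers, a difference of 0.2 of a patient. From the 35 that the inputs actually require, 35/0.9 = 38.9, so 39 enrolled would do and 42 more than covers it.

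**Conclusion.** The point holds, as a reporting error in two parts. The stated inputs require 35 sirolimus patients (33 by the normal approximation), not 38, and 38 gives power of about 0.84. The 0.8 is attached to 4.6, where a 5% test rejects with probability 0.05; it belongs to a true increase of 8.6.

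A reader might infer that the trial is underpowered, or that it accepts an 80% chance of discarding a drug that achieves the target. Neither follows. The discrepancy is conservative, and the 4-point distance behind the calculation is the right one wherever the sentence places it.

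The figures rest on SD 9.2, a one-sample one-sided 5% t-test of H0: mean increase ≤ 4.6, 38 patients analysed, and no interim stopping. The documents do not show whether 38 came from a larger SD, a higher power or a margin.

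**What to change.** Keep 42 and 14 enrolled. In Section 9.2, state the formula, the inputs and the origin of 38, and replace the power sentence with:

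> With 38 sirolimus participants, SD 9.2 and a one-sided 0.05 one-sample t-test of H0: mean increase ≤ 4.6, the probability of declaring futility is about 0.84 if the true mean increase is 8.6 and 0.05 if it is 4.6 (35 would suffice for 0.80), before any interim stopping.

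Align Section 9.4.2 at the same time, so that H0 is rejected on a t-test against 4.6 and not on the point estimate; without that, the quoted probabilities do not describe the trial's decision rule. The cost is wording in two sections, with no change to enrolment or assessments. The change in Section 9.4.2 does alter the stated decision rule, so it should be settled before the outcome data are unblinded.
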